The use of large sized particles of anorganic bovine bone matrix resulted in significantly more vital bone formation than small particle grafts ($26.77\% \pm 9.63\%$ vs $18.77\% \pm 4.74\%$, respectively) in a prospective randomized controlled clinical trial of bilateral sinus augmentations [22]. While the histomorphometric results of this study indicated a statistically significant increase in vital bone formation when the larger particle size was used, these findings were not shown in a previous maxillary sinus augmentation study where there was not a statistically significant difference in the percentage of new vital bone formation [23]. The authors related the difference between studies to the small sample size included in both (<15 patients). Due to the conflicting information and paucity of the literature on this topic, this proposed study will help shed the light on the influence of bone graft particle size on the amount of new bone formation in the most common bone defect in the oral cavity, i.e. the extraction socket, after ridge preservation.

3. Objectives/Specific Aims

The aim of the study is to clinically and histologically analyze the amount of the bone gained after ridge preservation procedures performed using small (250-1000 μ m) versus large (1000-2000 μ m) particle size bone cortico-cancellous allograft (Maxxeus™ Dental, Community Tissue Services, Kettering, OH) at time of implant placement, 3 months following surgical intervention.

Specific objectives include:

- A. To compare the bone quantity (bucco-lingual ridge width) between the two bone allograft particle sizes by direct clinical measurements
- B. To compare the bone quantity (bucco-lingual ridge width and apico-coronal ridge height) between the two bone allograft particle sizes by 3-dimensional radiographic measurements (CBCT scan)
- C. To evaluate the quality of bone regenerated with the use of the two bone allograft particle sizes via histological and histomorphometric analyses.

Primary outcome: histologic and histomorphometric bone core analyses (from the implant preparation site).

Secondary outcomes: clinical and radiographic dimensional changes of the edentulous ridges.

Null Hypothesis: Large-sized particle bone allografts will achieve similar histologic and clinical outcomes as small-sized particle allografts.

4. Materials and Methods

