Patients will be randomized on the day of surgery to receive either Small Particle (SP) (Group 1) or Large Particle (LP) bone allograft (Group 2) by permuted block randomization approach to ensure the same number of patients in each group, using computer-generated random number list. A course of prophylactic antibiotics will be dispensed at the time of surgery (Amoxicillin 2 g or Clindamycin 600 mg, 30 minutes to one hour prior to surgery). The graft material utilized for all surgical procedures, for all patients, will be obtained from one manufactured lot, from the same donor to account for variation in age, race, gender and related healing potential of different grafts (Maxxeus™ Dental, cortico-cancellous FDBA, Community Tissue Services, Kettering, OH). Following local anesthesia, tooth or teeth will be gently elevated using a minimally traumatic technique that prevents loss of supporting bone. Socket(s) will be curetted, irrigated and inspected following extraction and the presence of intact walls or minimal dehiscence ($\leq 3\text{mm}$) will be verified. The randomized bone allograft (SP or LP) will be hydrated in saline and then placed in the socket and covered with a collagen dressing. Vicryl sutures will be used to achieve stability of the collagen dressing over the graft material (Fig. 3). Standardized photographs will be taken to document the procedure.

[figure not shown]

Figure 3. **A.** Tooth is elevated, **B.** Extracted tooth, **C.** Socket is curetted, irrigated and inspected for presence of bone walls **D.** Graft is placed in the socket and covered with a collagen dressing and sutures.

Cone Beam Computed Tomography (CBCT) scan will be taken immediately after socket preservation and will serve for baseline measurements.

Post-surgical antibiotics will be prescribed for the first post-operative week and analgesics will be prescribed as necessary. All subjects will be dispensed Peridex® chlorhexidine mouth rinse and instructed to rinse twice daily for two weeks following the surgery, to help guard against possible infection. Verbal and written home care instructions will be provided.

Follow-up visit- Study visit 2

The sutures will be removed after two weeks. Surgical sites will be evaluated for healing status and postoperative instructions on resuming oral hygiene measures will be instructed to patients.

Bone Biopsy and Implant Placement - Study visit 3

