Using baseline and implant placement CBCT data, the 2 scans will be superimposed in a virtual implant planning software (coDiagnostix) to evaluate 3-D volumetric changes (in cc). In addition, a virtual tooth (planned in optimal position at the implant site) will serve as reference point for standardized assessment of 2-dimensional ridge width and height changes (in mm) from the time of grafting until time of implant placement.

Statistical Analysis

To reject the null hypothesis of equal means with a significance level (alpha) of 0.05 using a two-sided two-sample unequal-variance t-test, 22 patients in each group (total of 44) will be required to reach 0.90 statistical power. Accounting for 8-patient loss-to-follow up, 50 patients will be enrolled in the study.

A two-sample t-test was conducted to compare the difference between the two groups in terms of new bone formation. Both the clinical and the radiographic dimensional changes between the groups were evaluated using two-sample t-tests. A paired t-test was used to compare among all subjects the radiographic vertical loss at the facial, midline, and lingual of the crest. The correlation between the clinical and radiographic changes in width at the crest and the influence of the type of tooth site on the radiographic dimensional changes were evaluated with two-sample t-tests.

References

1. Cardaropoli, G., M. Araujo, and J. Lindhe, Dynamics of bone tissue formation in tooth extraction sites. An experimental study in dogs. *J Clin Periodontol*, 2003. **30**(9): p. 809-18.
2. Araujo, M.G. and J. Lindhe, Dimensional ridge alterations following tooth extraction. An experimental study in the dog. *J Clin Periodontol*, 2005. **32**(2): p. 212-8.
3. Nevins, M., et al., A study of the fate of the buccal wall of extraction sockets of teeth with prominent roots. *Int J Periodontics Restorative Dent*, 2006. **26**(1): p. 19-29.
4. Tan, W.L., et al., A systematic review of post-extraction alveolar hard and soft tissue dimensional changes in humans. *Clin Oral Implants Res*, 2012. **23 Suppl 5**: p. 1-21.
5. Jambhekar, S., F. Kern, and A.S. Bidra, Clinical and histologic outcomes of socket grafting after flapless tooth extraction: a systematic review of randomized controlled clinical trials. *J Prosthet Dent*, 2015. **113**(5): p. 371-82.

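### A paired t-test is named for comparing vertical loss at three crest positions; it handles only two, and testing all three pairs unadjusted would give about 9% to 12% false positives

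*Combined protocol and SAP*

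**What the plan says.** All references are to the extraction-socket protocol, the second of the two in the combined document.

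- **Position comparison (section 4, Statistical Analysis):** "A paired t-test was used to compare among all subjects the radiographic vertical loss at the facial, midline, and lingual of the crest". The section does not say which pairs are compared or at what significance level. It gives no overall test of position and no multiplicity adjustment. The three positions are named only in this sentence; the Clinical and Radiographic Measurements section refers to width and height change in general.
- **Arm comparison (the sentence just before it):** "Both the clinical and the radiographic dimensional changes between the groups were evaluated using two-sample t-tests".
- **Objective B (section 3):** "To compare the bone quantity (bucco-lingual ridge width and apico-coronal ridge height) between the two bone allograft particle sizes", measured on CBCT.
- **Outcome tier (section 3):** "Secondary outcomes: clinical and radiographic dimensional changes of the edentulous ridges".
- **Significance level:** 0.05 appears only in the sample-size statement, "with a significance level (alpha) of 0.05 using a two-sided two-sample unequal-variance t-test".
- **Numbers:** the same statement says "22 patients in each group (total of 44) will be required to reach 0.90 statistical power". Enrolment is set at 50, with an allowance of 8 losses.

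**The concern.** Facial, midline and lingual loss are three repeated measurements on one ridge. The named test takes two, so it cannot make the stated comparison. Whoever runs it must choose one, two or three pairs, and the text does not restrict that choice. The natural reading is that all three pairs are tested, each at 0.05.

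At stake is a claim about where on the crest height is lost. The protocol's own background says the buccal wall tends to resorb more than the lingual, so a reported difference between positions would look credible. It would carry a larger chance of error than its p-value suggests.

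**Working it through.** **The plan's own figure.** The plan states no error rate for the position comparison, so there is none to reproduce. Only its sample size enters the check.

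**Inputs**
- Positions: 3, hence 3 × 2 / 2 = 3 pairs (Statistical Analysis).
- Patients: 44, the planned analysed total. The stated enrolment and losses give 50 − 8 = 42, so 42 and 50 were also tried.
- Level: 0.05 two-sided for each pair. This is an assumption, because the plan attaches 0.05 only to the sample-size test.
- Correlations and SDs of the three measurements: not given, so a range is assumed.

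**Step 1. Reference value under independence.** For three tests, 1 − 0.95³ = 1 − 0.857375 = 14.3%. The three differences are not independent, because facial minus lingual equals (facial minus midline) plus (midline minus lingual). The true figure should be lower and needs simulation.

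**Step 2. Simulation.** For each scenario, 200,000 trials of normal data with equal true means were generated. Each pair was tested with t = mean difference / (SD of differences / √n) on n − 1 degrees of freedom. At a rate near 12% the simulation standard error is √(0.12 × 0.88 / 200,000) = 0.07 percentage points.

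The columns give the chance of at least one false positive: (a) three unadjusted tests at 0.05; (b) Bonferroni at 0.05/3, which equals Holm when no position differs; (c) a pair counted only if Hotelling's 2-df test is also significant. Correlations are in the order facial–midline, midline–lingual, facial–lingual.

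| Correlations | SDs | n | (a) | (b) | (c) |
|---|---|---|---|---|---|
| 0.5, 0.5, 0.5 | equal | 42 | 12.4% | 4.5% | 5.0% |
| 0.5, 0.5, 0.5 | equal | 44 | 12.3% | 4.4% | 4.9% |
| 0.5, 0.5, 0.5 | equal | 50 | 12.2% | 4.4% | 5.0% |
| 0, 0, 0 | equal | 44 | 12.4% | 4.5% | 5.1% |
| 0.8, 0.8, 0.8 | equal | 44 | 12.3% | 4.5% | 5.0% |
| 0.8, 0.8, 0.64 | equal | 44 | 11.9% | 4.3% | 4.9% |
| 0.7, 0.7, 0.4 | equal | 44 | 11.5% | 4.1% | 4.8% |
| 0.5, 0.5, 0.5 | facial 2× | 44 | 11.7% | 4.2% | 5.0% |
| 0.7, 0.7, 0.7 | facial 3× | 44 | 11.0% | 3.9% | 4.9% |
| 0.7, 0.7, 0 | equal | 44 | 8.9% | 3.2% | 3.8% |

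The number of patients hardly matters. The last row is an extreme case in which the midline value is almost determined by the other two. Column (a) runs from 8.9% to 12.4%; both remedies bring the rate to about 5% or below.

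**Step 3. Does the covariance in the replacement model matter?** It does. A model with only a patient random effect assumes equal variances and correlations. Its 2-df position test at n = 44 (100,000 trials), with facial, midline and lingual SDs in the ratio 1:3:1, rejected a true null 7.2% of the time at correlation 0.3 and 7.5% at 0.6. With unequal correlations the rate was about 7% to 8%. Hotelling's test or an unstructured covariance gives about 5%.

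**The case against.** The strongest reply is that this is a small wording gap. The plan does not say that all three pairs are tested, that each is tested at 0.05, or that adjustment is withheld. The position contrast is not among objectives A to C, and the outcome is secondary. All of this is true. It means the 9% to 12% is conditional, and that nothing in the primary analysis is at risk. It does not rescue the sentence, since a two-measurement test is still assigned to three measurements.

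A reader might also infer three stronger things that the documents do not support.

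- **That pooling the arms inflates the error.** It does not; the inflation comes from several unadjusted pairs. Asking where on the crest loss is greatest across all patients is a legitimate question, and pooling suits it.
- **That particle size is left out of the analysis of vertical loss.** The preceding sentence plans between-arm tests of radiographic change, and objective B includes ridge height. What is unstated is whether height is compared between arms at each of the three positions.
- **That omitting an arm-by-position test is an error, because it is the only analysis bearing on the trial's question.** Neither the objectives nor the null hypothesis asks whether particle size changes the pattern across positions. Equal extra loss at all three positions in one arm would produce no interaction, so that test could miss a real particle-size effect. Separate between-arm tests at each position would not formally test the interaction, but the plan does not claim that they do.

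**Conclusion.** The concern holds in a limited form. The stated test cannot make the stated comparison, and the plan leaves the choice of pairs and the error control open. The familywise error is about 9% to 12%, against a nominal 5%. This assumes that all three pairs are tested at 0.05 without adjustment, that no position truly differs, that the data are normal, and that there is one set of three measurements per patient. With near-equal correlations and SDs it is about 12%; strongly unequal correlations can bring it down to about 9%. Describing it as a fixed 12%, or as always more than double the nominal level, would go too far.

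The effect is confined to statements about facial, midline and lingual loss relative to one another. The between-arm comparisons, the primary histomorphometric outcome and the sample size are not touched. It is worth correcting because the method named is wrong and the remedy is cheap.

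**What to change.** Replace the sentence with the following.

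1. **Model.** Fit a repeated-measures model for radiographic vertical loss, with position (three levels) and arm as fixed effects and an unstructured covariance across the three positions. Hotelling's T-squared on the within-patient differences is a simpler alternative for the position test. A patient random effect alone is not enough (Step 3).
2. **Multiple sockets.** The surgical-visit text allows more than one tooth per patient. State how these are handled, for example by a socket level within patient.
3. **Testing.** Test position once, with 2 degrees of freedom. Then report facial–midline, midline–lingual and facial–lingual differences with confidence intervals and Holm-adjusted p-values. The ordered p-values are compared with 0.05/3 = 0.0167, 0.05/2 = 0.025 and 0.05.
4. **Particle size.** Keep the between-arm difference in height change as the result for objective B, and state at which position or positions it is assessed. An arm-by-position estimate with its confidence interval may be added, labelled exploratory. It is not among the stated objectives, and the analyses are already described in the past tense, so it would be post hoc.

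The cost is one paragraph of text and a re-run on measurements the plan already collects. Pairwise position p-values become slightly less favourable.

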Ridge preservation (socket grafting) at the time of tooth extraction is a commonly performed procedure that prevents extensive ridge resorption and allows for optimal implant placement. Ridge preservation can be achieved with different graft materials from autogenous, allogenic, xenograft, and alloplast sources. Due to its success in space maintenance, rapid turnover, biocompatibility, and the lack of need to harvest from another site, small-sized bone allograft materials (especially freeze-dried bone allografts, FDBA) have become increasingly popular. However, the effect of particle size on the clinical and histological outcomes following site preservation at the time of tooth extraction has not been well studied or reported in the literature. This randomized trial aims to clinically and histologically compare the amount and quality of the bone gained following ridge preservation procedures when using small (250-1000 μ m) versus large (1000-2000 μ m) particle size bone cortico-cancellous allografts at time of dental implant placement, 3 months following surgical intervention.

2. Introduction/Background

Studies have demonstrated that bone resorption occurs secondary to tooth extraction with the majority of dimensional changes occurring within the first 3 to 6 months [1-5]. The buccal wall of the socket (Fig. 1) tends to be resorbed to a greater degree than the lingual wall because the coronal aspect of the buccal plate is often comprised of bundle bone, a very thin layer (≤ 1 mm in most cases) of bone [6]. Cardaropoli et al. [1] reported a meaningful negative correlation between baseline buccal wall thickness and ridge width change at sites receiving tooth extraction but no ridge preservation procedures. Vertical height loss frequently accompanies the horizontal loss and usually is seen when multiple adjacent extraction sites are combined (Fig. 2). Some have described a loss of up to 50% of the overall ridge width without ridge preservation at time of tooth extraction [7].

[figure not shown]

Fig 1. A. Socket anatomy, **B.** Loss of buccal bone following tooth extraction.

Vertical height loss frequently accompanies the horizontal loss and usually is seen when multiple adjacent extraction sites are combined (Fig. 2). Some have described a loss of up to 50% of the overall ridge width without ridge preservation at time of tooth extraction [7].

[figure not shown]

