Patients presenting to the graduate periodontal clinic at the University of Alabama at Birmingham School of Dentistry will be screened according to the following criteria:

Inclusion criteria

- English speaking, able to read and understand informed consent document
- Hopeless non-molar tooth or teeth that are planned to be replaced with dental implants after ridge preservation
- Socket with residual 4 walls following minimally invasive tooth extraction (a dehiscence \leq 3 mm may be included)
- Healthy adjacent teeth must be present and not planned for extraction

Exclusion criteria

- Less than 18 years old
- Smokers/tobacco users (>10 cigarettes/day)
- Patients with systemic pathologies or conditions contraindicating oral surgical procedures or adverse affecting wound healing as uncontrolled diabetes
- Poor compliance risk (i.e., poor oral hygiene, history of alcohol or drug abuse)

To reject the null hypothesis of equal means with a significance level (alpha) of 0.05 using a two-sided two-sample unequal-variance t-test, 22 patients in each group (total of 44) will be required to reach 0.90 statistical power. Accounting for 8-patient loss-to-follow up, 50 patients will be enrolled in the study.

All clinical measurements are being taken by one experienced examiner blinded to the randomization process (small vs. large particles) before grafting and at time of implant placement. Another examiner will perform the radiographic evaluations and will also be blinded to the randomization process. Intra-examiner calibration will be conducted to ensure reliability of measuring method.

Screening/baseline visit:

Patients' medical history and electronic records will be reviewed. A treatment plan will be developed by an interdisciplinary team consisting of a periodontist and a restoring dentist and respective residents. Study examiners will conduct clinical and radiographic exams to determine eligibility according to the above criteria. If deemed eligible, study visits and objectives will be explained to all participants and IRB approved written informed consent will be obtained.

Surgical visit - Study visit 1:

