Three months' post-socket grafting, a second CBCT scan will be taken to evaluate the success of the grafting procedures and to plan the optimal implant position. The site(s) will be exposed for surgical placement of the implant(s). After exposure of the healed edentulous ridge, the implant sites will be located with the use of the surgical stent (prepared by the restoring dentist) and the ridge width will be measured at the crest and 4 mm apical to the crest with the same standardized caliper. If ridge width is deemed adequate, a dental implant of appropriate size will be placed. Prior to implant placement a bone biopsy will be taken from the implant site using a 2-mm internal diameter trephine. The biopsy will be stored in formalin and sent to the UAB Histomorphometry and Molecular Analysis Core for histomorphometric analysis.

[figure not shown]

Fig 4. A. Site after 3 months of healing, B. Flap elevation, C. Core biopsy trephine, D. Implant placement, E. Flap replaced and sutured.

Histomorphometric Analysis

Each specimen will be fixated with 10% neutral buffered formalin for 48 hours prior to be dehydrated and embedded in methylmethacrylate. It will be ground sectioned at the center of the biopsy in its long axis into 50-70 micron-thick sections (Exakt Technologies, Inc., Oklahoma City, OK), and polished with 4000 grit sandpaper and Novus Polish to create a surface as smooth as possible. All sections will be stained with Goldner's Trichrome stain and imaged for quantification of bone formation. Histomorphometry will be done using the Bioquant® Image Analysis Software (R&M Biometrics, Nashville, TN) by measuring the total surface of vital bone, residual graft particles, organic matrix and artifact/air components.

Corresponding percentages will be calculated for each of these tissues and compared between small and large particle grafts for ridge preservation and augmentation separately. These experiments will be conducted at the UAB Histomorphometry and Molecular Analysis Core and all measurements made by an experienced blinded lab technician.

Clinical and Radiographic Measurements

Direct measurements (in mm) of the bucco-lingual ridge width will be taken following tooth extraction at the largest area of the socket orifice, using a UNC-15 periodontal probe. This measurement will be repeated at time of implant placement, 3 months after socket preservation.

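### The extraction-socket SAP tests a correlation between clinical and CBCT width changes with a two-sample t-test, which answers neither an association nor an agreement question

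*Combined protocol and SAP*

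**What the plan says.** The last sentence of the Statistical Analysis section (extraction-socket protocol) has two subjects and one method. The first subject is "The correlation between the clinical and radiographic changes in width at the crest". The second, with the method for both, reads "the influence of the type of tooth site on the radiographic dimensional changes were evaluated with two-sample t-tests".

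The two quantities to be correlated are defined under Clinical and Radiographic Measurements:

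- **Clinical:** "Direct measurements (in mm) of the bucco-lingual ridge width will be taken following tooth extraction at the largest area of the socket orifice", repeated at implant placement three months later.
- **Radiographic:** the baseline and three-month CBCT scans are superimposed, and a virtual tooth "will serve as reference point for standardized assessment of 2-dimensional ridge width and height changes" in mm.

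Both are continuous, in the same unit, and taken on the grafted sites over the same healing period. The inclusion criteria allow more than one site per patient: "Hopeless non-molar tooth or teeth that are planned to be replaced with dental implants after ridge preservation". The status of these endpoints is given under Objectives/Specific Aims: "Secondary outcomes: clinical and radiographic dimensional changes of the edentulous ridges".

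**The concern.** A two-sample t-test asks whether two independent groups have the same mean. Here there are not two groups but two readings of each site. Two readings of the sentence are possible.

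- **Association** (do sites with a larger clinical change also show a larger CBCT change?). This is the ordinary meaning of the word and the one used in the protocol's own Introduction/Background, which says a cited study "reported a meaningful negative correlation between baseline buccal wall thickness and ridge width change". The t-test does not address it.
- **Agreement in mean change** (does the probe give the same average change as CBCT?). This is a question about means, but the data are paired and the test treats them as independent.

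A statement that clinical readings do or do not follow CBCT would rest on a p-value that does not measure association and that misstates the evidence on any mean offset.

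**Working it through.** The plan attaches no target coefficient, power or sample size to this analysis, so there is no figure of its own to reproduce. The check has three steps.

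**1. Can the text be read another way?** The comparison of small with large particles on clinical and radiographic changes has its own sentence earlier in the section, so this sentence is not that comparison. The sentence just before it names a paired t-test for another within-subject comparison, so the section does distinguish paired from two-sample. The usual significance test of a correlation uses a t statistic on n − 2 degrees of freedom, but that is not a two-sample t-test. No coefficient, regression, intraclass correlation or limits-of-agreement analysis is named elsewhere.

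**2. What the test responds to.** Let C and R be the clinical and radiographic change on one site, with common SD σ and correlation ρ, on n sites.

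- The numerator is mean(C) − mean(R). Its expected value is the offset between the methods and does not involve ρ.
- Its true variance is 2σ²(1 − ρ)/n. The two-sample test uses 2σ²/n.
- With no offset, the actual error rate at nominal 5% is therefore about 2[1 − Φ(1.96/√(1 − ρ))].
 - ρ = 0.3: 1.96/0.837 = 2.34, giving 1.9%
 - ρ = 0.6: 1.96/0.632 = 3.10, giving 0.2%
 - ρ = 0.9: 1.96/0.316 = 6.20, giving practically 0%

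With equal means, a stronger correlation makes a significant result less likely, the reverse of a correlation test.

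**3. Size by simulation.** From the documents: n = 44 (22 per group) and two-sided 0.05. Assumed: bivariate normal data, equal SDs, one site per patient, and the values of ρ and offset shown. Each row has 40,000 runs; entries are rejection rates.

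| ρ | Offset (SD) | Two-sample t (stated) | Paired t | Pearson |
|---|---|---|---|---|
| 0 | 0 | 5.2% | 5.2% | 5.0% |
| 0 | 0.25 | 20.9% | 20.7% | 5.2% |
| 0 | 0.5 | 64.0% | 63.0% | 5.0% |
| 0.3 | 0 | 2.0% | 5.0% | 51.4% |
| 0.3 | 0.25 | 17.0% | 27.5% | 51.7% |
| 0.6 | 0 | 0.2% | 5.1% | 99.4% |
| 0.6 | 0.25 | 11.1% | 44.5% | 99.4% |
| 0.9 | 0 | 0.0% | 4.8% | 100% |
| 0.9 | 0.25 | 1.5% | 95.3% | 100% |

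The zero-offset rows match the formula in step 2. With 42 patients (50 enrolled − 8 lost) the picture is the same:

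- ρ = 0, offset 0.5 SD: stated test 62.2%, Pearson 5.1%
- ρ = 0.9, no offset: stated test 0.0%, Pearson 100%
- ρ = 0.9, offset 0.25 SD: stated test 1.3%, paired test 94.5%

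**The case against.** The strongest reply is that this is a wording error. Two analyses were merged under one verb, the method fits the second if tooth-site type has two categories, and the authors clearly knew the paired test. A coefficient may have been computed correctly and described badly. That is possible, and the documents cannot show which test was run. But the method then stands nowhere in the plan, so the text needs correcting either way.

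Other points stand in part:

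- **Agreement is not mentioned in the plan.** Association is the more natural reading. On the agreement reading the stated test is not liberal at the non-negative correlations examined: it matches the paired test at ρ = 0 and is conservative above that. The cost is lost power, so a non-significant result would be weak reassurance that the methods match.
- **The simulation is illustration.** Every ρ and offset is assumed, and the Pearson comparison sets tests of different null hypotheses side by side. It shows what the test responds to, not a measured harm to this trial.
- **An offset is only plausible.** The two methods use different reference points, but a fixed difference in location cancels in a change score unless resorption differs between the locations.
- **The clinical measurement is itself described in two ways at re-entry.** Study visit 3 has a caliper reading at the crest and 4 mm below it; Clinical and Radiographic Measurements has a repeat of the probe reading at the socket orifice. The correction must say which one enters the analysis.

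**Conclusion.** The concern holds. As written, the test is wrong for association and wrong for paired agreement, and this follows from the text without any assumed number. The assumed values bear only on the size: the stated test can be significant in 64% of trials with no correlation at all (0.5 SD offset), and in none with a correlation of 0.9 (no offset).

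The reach is small. This is an ancillary analysis of secondary outcomes, outside objectives A to C. The error does not touch the primary histomorphometric comparison, the between-arm tests or the sample size. It should be corrected, but it does not threaten the trial's main conclusions.

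**What to change.** Split the sentence in two and state which question the first half asks.

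- **Association:** report the Pearson (or Spearman) coefficient between clinical and CBCT change in crestal width, with a 95% confidence interval. At 44 pairs with one site each, the Fisher-z interval would be 0.00 to 0.55 for r = 0.3, 0.37 to 0.76 for r = 0.6, and 0.82 to 0.94 for r = 0.9.
- **Agreement:** report the mean paired difference with a 95% confidence interval, plus Bland-Altman limits. In SDs of one method, the interval half-width and the half-width of the limits would be 0.36 and 2.32 at ρ = 0.3, 0.27 and 1.75 at 0.6, and 0.14 and 0.88 at 0.9.
- **Tooth-site type:** keep the two-sample t-test only for a comparison of two categories, and name them.

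Use all measured sites, so that none has to be chosen after the fact. Where a patient contributes more than one, obtain the intervals by resampling whole patients. In a check with 44 patients, of whom 0, 5 or 11 gave two sites, percentile intervals covered 0.918 to 0.935 for r and 0.930 to 0.948 for the mean difference. That is slightly below 0.95 and should be disclosed. Name the clinical measurement used, and say whether the coefficient is pooled over arms or within arm, since an arm effect on both measurements would raise a pooled coefficient.

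Because the section is written in the past tense, label the change as a correction made after the data were analysed. The cost is one or two lines of SAP text and a re-run on existing data, with no new visits or measurements.
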